### **Descriptive and Process Measures**

Demographic variables and cancer history and treatments will be measured at baseline by an in-house questionnaire. Measures that account for disease extent (presence or absence of metastatic disease), type of ADT (intermittent vs. continuous; use of next generation high potency agents) will be collected. Updated information will be collected at subsequent visits. Measures of weight and height will also be made.

Presence of chronic medical conditions that affect physical functioning will be measured by the Charlson Comorbidity Index and the Functional Comorbidity Index (FCI) [80]. We use both instruments because Charlson provides an index of “sickness” that is commonly reported in studies of older adults, while the FCI provides a different index of the number of conditions that affect a persons physical functioning. We will add two additional conditions to the list of 18 in the FCI to capture vestibular problems and/or peripheral neuropathy that might affect exercise ability and predispose men to fall risk in excess of ADT so that we can control for this in analyses.

Exercise outside the exercise intervention could affect the fall and function outcomes in our study. In addition to using CHAMPS to measure physical activity for the frailty criterion and exercise participation during follow-up, we will also look at individual items to see whether participants significantly increase participation in other types of exercise in addition to their assigned study program.

Adherence. Adherence (% of prescribed sessions completed) will be tracked from attendance logs recorded by the exercise instructor. Adherence data will be used to describe the dose of exercise received by participants. It is expected that men will occasionally miss classes due to travel, illness, or other reasons, thus we must get an accurate estimate of received (exercise) dose in order to generalize our findings.

Acceptability of intervention and self-management of ADT side effects is useful information to guide future dissemination and implementation efforts. We will survey prostate cancer survivor's knowledge of and intent to manage ADT side effects [81] at baseline and assess satisfaction with each exercise program post-intervention [82].

### **Additional Measures of Interest**

Fear of falling may impact a participant's confidence that he can safely engage in a study exercise program. This factor may also change across the intervention. Though this is not a major outcome in the proposed study, we feel it may provide important information about the population and intervention. To assess fear of falling we will use the Survey of Activities and Fear of Falling in the Elderly (SAFFE), [83] that has 11 items representing activities of daily living associated with fear of falling, mobility, and social activities. The SAFFE score is the average of item responses, with higher scores indicating greater fear of falling.

Perceived disability. Though not a specified endpoint for this trial disability and dependence upon others for daily tasks may result from frailty and dysfunction. If either experimental intervention reduces frailty and improves function it may also lower the risk for disability, so that prostate cancer survivors on ADT can remain more independent. We will measure perceived disability using the 16-item disability component of the Late-Life Function and Disability Instrument [84, 85]. Scores range from 0-100, with higher scores indicating less disability.

Cancer treatment related symptoms. Several symptoms that are associated with ADT may impact both exercise tolerance and/or fall risk, but are also possibly ameliorated by exercise. Thus, we will track changes in symptoms across the study to examine whether or not these symptoms moderate or mediate the effects of the different interventions on falls and frailty. All measures will use standardized and widely accepted questionnaires that are cancer-specific when available. The symptoms and their measures include fatigue by the Functional Assessment of Cancer Therapy (FACT) fatigue instrument, pain by the Brief Pain Inventory, vertigo by the Vertigo Symptom Scale, cognition by the FACT-Cog instrument, Anxiety by the PROMIS short form anxiety instrument and Depressive symptoms by the Centers for Epidemiologic Studies Depression scale (CES-D).

Cancer-related loneliness: Participation in group-based exercise may facilitate development of friendships and comradery with others around a shared experience of cancer, which may result in reduced feelings of loneliness. To assess changes in cancer-related loneliness, we will administer a validated cancer-related loneliness questionnaire, the Cancer Loneliness Scale Adams, 2017, to survivors. We will administer the CLS to newly enrolled participants.

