## Outcome Measures

### Primary Endpoint: Falls

In this study, a fall is defined as unintentionally coming to rest on the ground or at some other lower level, not as a result of a major intrinsic event (e.g., stroke or syncope) or overwhelming hazard [13]. Falls over one year prior to baseline will be ascertained to characterize the sample and check for equality of randomization. Prospective assessment of falls will be done using the current gold standard of collecting monthly reports [45] returned by postal and/or electronic mail, an efficient (1-2 minute completion time) and effective method used by our team and others [41, 46-48]. In two prior studies we obtained 98% of monthly fall reports over 6 months [46, 49]. Participants will be provided with a monthly falls calendar to record falls when they occur, in order to reduce issues of recall and false negatives. Each participant that records a fall will be phoned to confirm that each fall meets the standard definition in order to reduce the risk of false positives, and to obtain information about the fall (e.g., how it occurred) and any resultant injury. An “injurious” fall is one that results in fractures, head injuries, sprains, bruises, scrapes, or serious joint injuries, or where the participant seeks medical care [13]. Of primary interest in the proposed study is the # of falls, with the # of injurious falls and medical care resulting from a fall being used for descriptive purposes of the study population.

Secondary Endpoint: Frailty will be measured using the components of the Frailty Phenotype [29]. The original 5 criteria of the phenotype (shrinking, exhaustion, low activity, slowness, and weakness) were limited to the measures available in the Cardiovascular Health Study [29]. The phenotype can now be measured more accurately with objective measures (e.g., lean body mass rather than self-report weight loss[50]). In this study, we will assess each frailty component using measures that will most accurately capture frailty criteria in the prostate cancer survivor population and where cutoff scores can be appropriately determined. A total frailty score will be calculated in the same manner as that of Fried:  $\geq 3$  criteria = frail; 1-2 criteria = prefrail; 0 criteria = robust. Since each variable is a continuous measure we will examine changes in each individual frailty component to determine how each intervention may shift frailty among our sample. Criteria are measured as follows:

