2. *Exhaustion*: We will use the self-reported score on SF-36 Vitality Scale which we have used to characterize exhaustion for frailty in cancer survivors [56] and which has established reliability [57], has been validated in cancer survivors as a fatigue measure[58] and has shown sensitivity to change in response to exercise in adult, older adult and clinical populations, including cancer [59-61]. We will use cutpoints of scores of less than 50.00 (normed) for prostate cancer survivors aged 50-64 years or scores less than 40.00 (normed) for prostate cancer survivors aged 65+ years. Cutpoints are lowest quartile of scale in general U.S. population [57]. The Functional Assessment of Chronic Illness Therapy (FACIT) Fatigue scale will also be administered. It is a 13-item questionnaire. Though not used in frailty assessment, but used to evaluate reductions in cancer-related fatigue from exercise [62], we can also consider changes in the fatigue subscale of the QLQC30 which could be more sensitive in prostate cancer survivors (see below).
3. *Low Activity*: Low activity will be measured by physical activity-related energy expenditure (METS), calculated from self-report physical activity. We will use Fried's original cutpoints for "low activity": <383 kcals per week spent in moderate-vigorous intensity activity measured by the 41-item Community Healthy Activities Model Program for Seniors (CHAMPS) physical activity questionnaire. [63] CHAMPS is a common and highly reliable [64] measure of physical activity in older adults, including our studies in cancer survivors [33, 49, 65, 66]. We considered using accelerometry to track activity levels but this technique introduces considerable expense and personnel resources. Given our available resources we will be able to conduct a sub-study on 2 study waves (~100 men) to compare objective to self-report methods for tracking activity change over time.
4. *Slowness*: Walking speed will be measured as the fastest time of two 15' walks at a usual pace. Walks will be performed on an electronic gait mat to ensure accurate timing. We will use Fried's original cutpoints for "slowness" in older men of time  $\geq 7$  seconds for height  $\geq 173$  cm or time  $\geq 6$  seconds for height  $< 173$  cm. Test-retest correlations for average walk speed are strong: 0.72-0.93[67]. 3 meter Timed Up and Go will also be collected as a measure of slowness.

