#### Cognitive aging measures (Aim 1 and 2):

Cognitive functioning will be assessed using cognitive function subscale of the European Organization for Research and Treatment of Cancer Quality of Life Questionnaire (EORTC QLQ-C30; version 3, App. I) and the FACT-Cog Instrument.

Depression will be assessed using the Centers for Epidemiologic Studies Depression scale (CES-D).

Fatigue will be assessed using the self-reported score on SF-36 Vitality Scale and the Functional Assessment of Chronic Illness Therapy (FACT) Fatigue scale.

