### **Additional Analyses**

Injurious falls: Though the proposed study is not powered to examine reductions in injurious falls from the intervention, we will conduct an additional analysis on this important outcome. An injurious fall is one that results in fractures, head injuries, sprains, or serious joint injuries, or in a participant seeking outside medical attention. We will conduct this analysis among the subsample that had at least 1 fall using logistic regression.

Mechanisms of intervention effects on falls: We can use strength and stability measures to identify the mechanism(s) by which each exercise approach may reduce falls, strengthening support for exercise as a fall prevention strategy. We will test 3 mediators, muscle strength (chair stand time) and stability (walk speed and postural sway) as possible mediators because both measures may be affected by each intervention and each possible mediator is a major risk factor for falls. Mediation of the intervention effect by changes in performance measures will be analyzed using Mplus. A manifest model will be tested with the dummy vectors representing tai ji quan and strength training as exogenous variables, change in strength and as endogenous variables (mediators), and number of falls over the intervention period as an endogenous variable (outcome). Significant indirect parameter estimates based on standard errors using the multivariate delta method from the treatment variables to number of falls through changes in strength and stability would provide support for mediation.

Potential moderators of sustained exercise after the intervention: Linear and logistic regression models will be used to explore different predictors (e.g., age, comorbidities, timing of ADT, etc.) of adherence to exercise after structured training stops.

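### Fatigue is to be examined as a mediator of the effect on frailty, but fatigue is also scored inside frailty, so apparent mediation is inflated if exercise improves fatigue

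*Combined protocol and SAP*

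**What the plan says.** Section 3.0, Additional Measures of Interest (Cancer treatment related symptoms), says that symptoms will be followed "to examine whether or not these symptoms moderate or mediate the effects of the different interventions on falls and frailty". Fatigue comes first in the list: "The symptoms and their measures include fatigue by the Functional Assessment of Cancer Therapy (FACT) fatigue instrument". The Schedule of Events lists the scale as FACIT-Fatigue.

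Section 3.0, Secondary Endpoint: Frailty, counts five criteria: shrinking, exhaustion, low activity, slowness and weakness. Three or more make a man frail, one or two prefrail, none robust. On the exhaustion criterion: "We will use the self-reported score on SF-36 Vitality Scale which we have used to characterize exhaustion for frailty in cancer survivors". The same item says that this scale "has been validated in cancer survivors as a fatigue measure". It says of FACIT-Fatigue: "Though not used in frailty assessment, but used to evaluate reductions in cancer-related fatigue from exercise".

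The measures for Ancillary study #2 put both scales under one heading: "Fatigue will be assessed using the self-reported score on SF-36 Vitality Scale", together with the FACIT scale.

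Section 13.0, Additional Analyses, specifies one mediation model. Its outcome is the number of falls, its test is a delta-method test of the indirect effect, and its mediators are physical: "We will test 3 mediators, muscle strength (chair stand time) and stability (walk speed and postural sway) as possible mediators". No model is given for symptoms as mediators of frailty. Nothing says that exhaustion will be left out of the frailty score when fatigue is the mediator.

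**The concern.** A mediation analysis asks whether the intervention changes the outcome by way of the mediator. Here the proposed mediator (FACIT-Fatigue) and one fifth of the outcome criteria (Vitality below a cut) measure the same construct by the protocol's own account. An association between fatigue and the frailty score is therefore expected even if fatigue does nothing to the other four criteria. If an exercise arm also lowers fatigue, which the protocol regards as possible, the two paths combine into an indirect effect that looks like a mechanism.

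The risk is a misleading mechanism statement: that exercise reduces frailty by relieving fatigue, when all that happened is that the exhaustion item improved. Exhaustion alone can move a man from robust to prefrail, or from prefrail to frail, so the problem carries over to the three-level category. No aim, hypothesis, power calculation or arm comparison depends on this analysis.

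**Working it through.** The plan gives no figure for this analysis, so there is none to reproduce. The check is how often mediation would be declared when fatigue affects none of the other four criteria.

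**Inputs**
- 100 evaluable men per arm: Section 13.0, Power and Sample Size. One exercise arm against control.
- Not in the documents, so assumed: correlation r between FACIT-Fatigue and Vitality of 0.50, 0.70 or 0.85; effect d on both fatigue scales of 0, 0.2, 0.4 or 0.6 SD; control prevalences of 20% shrinking, 25% exhaustion, 25% low activity, 15% slowness and 35% weakness.

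**Model.** T is the arm, M is FACIT-Fatigue and Y is the number of criteria met. Exhaustion is Vitality below the cut that gives 25%. The other four criteria are independent of fatigue and of arm.
- Path a: M = i1 + aT + e
- Path b: Y = i2 + c'T + bM + e
- Delta-method test: |ab| / sqrt(a²·SE_b² + b²·SE_a²) > 1.96
- Joint test: a and b each significant at two-sided 0.05

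**Path b by hand, r = 0.70, d = 0.** The cut is at -0.674 SD, where the normal density is 0.318. So b = -0.70 × 0.318 = -0.222. Var(Y) = 0.16 + 0.1875 + 0.1875 + 0.1275 + 0.2275 = 0.89. Residual variance = 0.89 - 0.222² = 0.841. SE_b = sqrt(0.841/200) = 0.0648. The expected z is 0.222/0.0648 = 3.43, so path b is significant with probability Φ(3.43 - 1.96) = 0.93. Simulation gave 92.6%.

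**Path a by hand, d = 0.4.** z = 0.4 / sqrt(2/100) = 2.83, probability Φ(0.87) = 0.81. Simulation gave 80.3%.

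**Simulation, 3,000 trials per row, % significant**

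| r | d | Path b, five criteria | Indirect, five criteria, delta | Indirect, five criteria, joint | Indirect, four criteria, delta |
|---|---|---|---|---|---|
| 0.50 | 0 | 66.1 | 0.4 | 2.9 | 0.0 |
| 0.50 | 0.2 | 61.4 | 5.4 | 18.4 | 0.0 |
| 0.50 | 0.4 | 55.2 | 23.5 | 44.3 | 1.3 |
| 0.50 | 0.6 | 49.4 | 37.0 | 48.6 | 2.4 |
| 0.70 | 0 | 92.6 | 1.4 | 4.2 | 0.0 |
| 0.70 | 0.2 | 88.1 | 12.0 | 25.9 | 0.1 |
| 0.70 | 0.4 | 82.5 | 46.0 | 66.5 | 0.9 |
| 0.70 | 0.6 | 77.4 | 64.3 | 76.4 | 2.4 |
| 0.85 | 0 | 98.9 | 2.0 | 4.8 | 0.0 |
| 0.85 | 0.2 | 96.8 | 18.0 | 30.0 | 0.3 |
| 0.85 | 0.4 | 94.7 | 59.5 | 76.5 | 0.9 |
| 0.85 | 0.6 | 90.8 | 82.4 | 89.9 | 2.4 |

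With four criteria, path b is significant in about 5% of trials throughout, and the joint test in 0.2 to 5.3%.

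**Narrower range, adjusted for baseline FACIT-Fatigue.** With 30% exhausted, a correlation of 0.6 between baseline and 6-month fatigue, and 2,000 trials per scenario, the delta test gave 12, 24, 20, 41, 31 and 57% for (d, r) = (0.3, 0.60), (0.3, 0.75), (0.4, 0.60), (0.4, 0.75), (0.5, 0.60) and (0.5, 0.75). Four criteria gave 0.3 to 1.7%. A further run with its own assumed inputs gave 21 to 63%, against about 1 to 3%.

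**Three-level category.** With robust, prefrail and frail as the outcome (linear approximation), two sets of runs gave 8 to 45% and 16 to 51%.

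**Moderation.** The arm by baseline-fatigue interaction was significant in about 5 to 7% of trials, near the nominal 5%.

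**The case against.** The strongest reply has four parts.

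First, the mediator is not the criterion. FACIT-Fatigue is expressly kept out of the frailty score, and exhaustion is one dichotomised item among five. This is correct and matters: the overlap is of construct, not of scale. It lowers the correlation below 1 without removing it, and the assumed r allows for that.

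Second, no such analysis is modelled. The delta-method test in Section 13.0 is planned for falls only, with physical mediators. That stands: the figures above show what happens if that test is carried over to frailty. The stated intention remains, without a model and without a safeguard.

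Third, frailty is analysed in Aim 2 as three categories, not a count. The artefact is smaller there but does not disappear.

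Fourth, the plan will also examine each frailty component by arm, so readers could see if only exhaustion moved. This helps, but it does not correct the mediation estimate itself.

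Two stronger readings are tempting. A reader might infer that mediation will be found by construction. The plan does not imply that: only the fatigue-to-frailty path is built in, and the indirect effect also needs an intervention effect on fatigue. A reader might also infer that the moderation analysis fails because only men exhausted at baseline can improve on that criterion. That overlooks that men not exhausted at baseline can worsen, and the interaction test stays near its nominal level.

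**Conclusion.** The concern holds as a partial circularity, limited to fatigue as mediator and frailty as outcome. When exercise improves fatigue by 0.3 to 0.5 SD and the two scales correlate at 0.60 to 0.75, a delta-method test would report mediation in roughly 10 to 60% of trials in which fatigue affects no other criterion (about 8 to 50% for the three-level category). Leaving exhaustion out brings this to about 0 to 3%. With no effect on fatigue, the five-criterion rate is 0.4 to 2.0% by the delta method and at most 4.8% by the joint test, so there is no inflation.

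The percentages depend on correlations, effects and prevalences that the documents do not give. The direction of the bias does not depend on their exact values, provided the two scales correlate and exercise improves fatigue. Severity is minor: this is one exploratory intention, for one symptom and one of two outcomes.

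**What to change.** In Section 3.0, Additional Measures of Interest, add one sentence: when fatigue is examined as a mediator of the effect on frailty, the outcome is a score from shrinking, low activity, slowness and weakness, or those components one by one. State the model for this analysis in Section 13.0. Leave the five-criterion category in the Aim 2 arm comparisons, and leave the moderation analyses and fatigue as a candidate mediator for falls unchanged.

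The cost is one derived variable and a short addition to the text; no new data are needed. The four-criterion score is not the published phenotype, but it would be used only here.

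The change removes the overlap and nothing else. If fatigue and the other criteria share a common cause (assumed correlation 0.2 with underlying fatigue, r = 0.70, d = 0.4), the delta test is still significant in 42.0% of trials with four criteria, against 75.8% with five. The result should therefore still be reported as exploratory, with that ordinary confounding acknowledged.

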### **Ancillary study:**

#### **Design**

This cross-sectional study will consist of collecting up to 7 days of daily mobility via Smartsox and relating mobility characteristics to ADT history, falls in the previous 12 months, objectively measured and self-report frailty, and objectively measured and self-report physical functioning in PC survivors exposed to ADT.

#### **Participant incentive**

There will be a \$25 remuneration to offset transportation costs for the testing visit.

#### **Measures and Data Collection**

Performance testing, frailty measures, and surveys will be administered once. Daily mobility will be collected for up to 7 days. Total time for performance testing and survey completion is ~2 hours. Men complete written surveys on a desktop or laptop computer, unless they prefer to complete paper surveys (~5% of participants in our last intervention trial prefer paper over online). Staff reviews surveys for completeness and follows up with participants in person or by phone on missing data.

#### **Outcome Measures**

**Daily mobility:** Subjects will wear SmartSox (APDM) with inertial sensors embedded into thin, neoprene ankle wraps. The sensors will be worn 8-10 hours a day for up to 7 consecutive days. At the end of the sampling period, participants will return socks to the study team in a pre-paid mailer. Raw data will be stored on the sensors and uploaded to a secure server for analysis after mailed back so wireless access is not necessary. Measures of mobility calculated during daily monitoring include turning quality, activity, and gait quality, and are calculated with proprietary algorithms from APDM. The measures are calculated by combining the 3 axes of linear acceleration with 3 axes of angular velocity and the magnetometer to obtain orientation of the limb in space. Wireless synchronization, unique to the APDM Opal sensors, allows precise temporal binding of data across limbs. Walking bouts and turning events are first identified, followed by calculation of metrics within each walking bout and turning event. Participants will document SmartSox use in a daily diary (i.e., date, time put on and taken off each day).

*Fall history:* Falls in the last year and injuries from falls will be collected using a falls survey.

*Frailty:* The five components of the frailty phenotype (shrinking, exhaustion, low activity, slowness, and weakness) will be collected using the following measures (described in detail above):

Shrinking – Lean mass as assessed by DXA and BIA

Exhaustion – Self-reported score on the SF-36 Vitality Scale, FACIT Fatigue scale

Low activity – measured by physical activity-related energy expenditure (METS), calculated from self-report physical activity. We will use Fried's original cutpoints for "low activity": <383 kcals per week spent in moderate-vigorous intensity activity measured by the 41-item Community Healthy Activities Model Program for Seniors (CHAMPS) physical activity questionnaire.

Slowness – Walking speed, measured as the fastest time of two 15' walks at a usual pace. 3 meter Timed Up and Go will also be collected as a measure of slowness.

Weakness – Timed chair stand test (seconds required to rise from chair 5 times)[68, 69].

We will also assess frailty using the FRAIL scale self-report measure, as we have done in our previous study [8].

*Demographic* variables and cancer history and treatments will be measured by an in-house questionnaire. Measures that account for disease extent (presence or absence of metastatic disease), type of ADT (intermittent vs. continuous; use of next generation high potency agents) will be collected.

*Objective physical functioning* will be assessed using measures of functional mobility and functional balance, as described above.

*Perceived physical functioning* will be measured by self-report using the physical function subscale of the European Organization for Research and Treatment of Cancer Quality of Life Questionnaire (EORTC QLQ-C30; version 3, App. I),

*Perceived disability* will be measured using the 16-item disability component of the Late-Life Function and Disability Instrument, as described above.

*Presence of chronic medical conditions* that affect physical functioning will be measured by the Charlson Comorbidity Index, as described above.

Other measures: User experiences while wearing SmartSox will be collected with a SmartSox User Questionnaire.

